13.1.6. Appendix F Study Exit Form

for your symptoms? (y/n)

Study Exit

	1. Please rate your overall experience with the test product.											
Po	0 oor		1	2	3	4	5 Neutral	6	7	8	9	10 Excellent
	1a.	Wł	ny? (f	ree res	sponse)							
	2.	Do	you f	feel th	at the t	est pr	oduct helpe	d wit	th your	indiges	tion a	and heartburn?
No	0 ot at		1	2	3	4	5 Neutral	6	7	8	9	10 definitely
	3.	Но	w like	ely are	you to	recon	nmend the t	est p	roduct	to your	frien	ds or family members?
No	0 t Li		1	2	3	4	5 Neutral	6	7	8	9	10 Extremely Likely
	4.		-			-	oduct helpe and upset s	-	-	cope w	ith o	ccasional heartburn,
No	0 ot at		1	2	3	4	5 Neutral	6	7	8	9	10 definitely
	5.			•	_		you would li stency, or o				•	vour experience with the ponse)
	6.	Dic	the t	test pr	oduct h	nelp p	revent you f	rom	having	to take	any a	alternative medication

13.1.7. Appendix G Adverse Event Form

Upset Stomach AE document

- 1. Did you experience any side effects after taking the test product? Y/N
 - a. If so, did you experience any of the following
 - o itching, rash, hives, throat/lip/tongue swelling, wheezing
 - low blood pressure, fainting, chest pain, shortness of breath, palpitations, irregular heart beat
 - o severe, persistent nausea, vomiting, diarrhea, or abdominal pain
 - o difficulty urinating, decreased urination
 - o fatigue, appetite loss, yellowing skin/eyes, itching, dark urine
 - severe joint/muscle pain
 - o slurred speech, one-sided weakness of face, arm, leg, vision
 - o abnormal bleeding from nose or gums
 - o blood in urine, stool, vomit,
 - o marked mood, cognitive, or behavioral changes, thoughts of suicide
 - o Other:
- 2. Please give a description of the event
- 3. How soon after taking the test product did you experience the side effect?
- 4. What did you do to alleviate the side effect?
- 5. Did you have to go to the hospital or see a doctor for this side effect?
 - a. Please describe any diagnosis or treatment that they provided.
 - b. If you were seen in the hospital, please upload any discharge paperwork or other documents from the hospital.

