- After completing the surveys, the participant will take the test product. The participant will take
 2 capsules per indigestion and heartburn episode. With a max of 6 capsules per day. (If
 participant takes 6 capsules in 1 day this will be defined as 3 indigestion and heartburn episodes
 and the participant will be exited from the study).
- After taking the test product, the participant will complete a 4-point Likert scale assessment for each symptom at 15 minutes, 30 minutes, and 1 hour after taking the test product.
- When the participants symptoms have resolved , the participant will complete the symptom diary.
- If the participant takes any other medication outside of the test product, the participant will record this on the symptom diary.
 - The participant is allowed to take alternative medications or supplements AFTER 1 hour from taking the test product.
- After taking the test product, the participant will be instructed to fill out an Adverse Event form for any side-effects experienced.
- After the first episode of indigestion and heartburn, the participant will be asked to complete the same process for another 2 episodes within the 60-day study time frame; however, these are not required.
- If the participant completes the required assessments for a total of 3 episodes of indigestion and heartburn, they will be prompted, by email, to exit the study.
- If the participant only completes the required assessments for the required 1 episode of indigestion and heartburn, the participant will be prompted, by email, to complete the study exit form and will be exited from the study on day 60 (60 days from the day of receipt of the test product).
- Neither the sponsor nor Hawthorne Effect Inc. will not collect any unused test product.
- Upon receipt of study exit survey and review of completed study forms, participant will receive an Amazon gift card of \$25 via email.

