6.2. Study Schedule of Activities

Assessments	Screening	Consent	Before Receipt of Test Product	Test Product Received	Event 1	15 Minutes After Event Start	30 Minutes After Event Start	60 Minutes After Event Start
Study Window								
Screening Survey	X							
Consent		X						
Baseline Survey			X					
Demographics			X					
Acknowledgement of receipt of test product				X				
Symptom Diary					X			X
4-point Likert Scale					X	X	X	X
Test Product Consumed					X			
Medications & Supplements			X					
AE Assessment					X	X	X	X
Study Exit Survey								

Assessments	Event 2	15 Minutes After Event Start	30 Minutes After Event Start	60 Minutes After Event Start	Event 3	15 Minutes After Event Start	30 Minutes After Event Start	60 Minutes After Event Start	Study Exit
Study Window									
Screening Survey									
Consent									
Baseline Survey									
Demographics									
Acknowledgement of Receipt of Test Product									
Symptom Diary	X			X	X			X	
4-point Likert Scale	X	X	X	X	X	X	X	X	
Test Product Consumed	X				X				
Medications & Supplements									
AE Assessment	X	X	X	X	X	X	X	X	X
Study Exit Survey									X

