6.4. Adverse Event and Safety Monitoring

Adverse Events (AEs) are defined as any untoward medical occurrences described by the study participant. All AEs will be self-reported and documented on the platform. The AEs will be reviewed by the study team including the remote trial coordinator and study principal investigator and reported according to the IRB requirements. Participants who experience adverse events will be advised to seek medical attention.

In the event that a participant experiences an adverse event, the clinical study manager or clinical ops coordinator will notify both the PI and Sponsor. The Sponsor will take appropriate action according to their standard operating procedures for any adverse events that warrant action by the sponsor.

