6.4.2. Adverse Event Relationship

Each reported AE will be assessed by the Investigator for relatedness, severity and causality.

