Dain or Discomfort in the	Unner Abdemen				
Pain or Discomfort in the	Opper Abdomen	2	3		
No Symptom	Slight	Moderate	Severe		
Burning in the Upper Ab	domen				
0 No Symptom	1 Slight	2 Moderate	3 Severe		
Pain/Burning in the center	er of your chest				
0	1	2	3		
No Symptom	Slight	Moderate	Severe		
Nausea					
0	1	2	3		
No Symptom	Slight	Moderate	Severe		
Vomiting					
0	1	2	3		
No Symptom	Slight	Moderate	Severe		
Burping					
0	1	2	3		
No Symptom	Slight	Moderate	Severe		
Other:	1	2	3		
0 No Symptom	Slight	Moderate			
No Symptom	Stight	Woderate	Severe		
60 Minutes afte	er taking the	e test product			
Bloating					
0	1	2	3		
No Symptom	Slight	Moderate	Severe		

Early Fullness During a Meal 0 No Symptom	1 Slight	2 Moderate	3 Severe		
Pain or Discomfort in the Upp 0 No Symptom	oer Abdomen 1 Slight	2 Moderate	3 Severe		
Burning in the Upper Abdom 0 No Symptom	en 1 Slight	2 Moderate	3 Severe		
Pain/Burning in the center of 0 No Symptom	your chest 1 Slight	2 Moderate	3 Severe		
Nausea 0 No Symptom	1 Slight	2 Moderate	3 Severe		
Vomiting 0 No Symptom	1 Slight	2 Moderate	3 Severe		
Burping 0 No Symptom	1 Slight	2 Moderate	3 Severe		
Other: 0 No Symptom	1 Slight	2 Moderate	3 Severe		
After your symptoms resolveplease complete any of the following questions if applicable.					
Did your symptoms resolve completely with the test product? Yes No Time of complete symptom resolution:					

Did you need to take another medication	on: Yes N	No
Medication #1:	Dose:	Time:
Medication #2:	Dose:	Time:
Medication #3:	Dose:	Time:
Did your symptoms resolve completely	with taking your altern	native medication? Yes No
After taking the alternative medication,	, time of complete resol	lution of symptoms:

Did you experience any side effects after taking the test product? (Y/N) If yes, **Please fill out** the Adverse Event form.

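### The adverse event prompts ask only about side effects, which is narrower than the protocol's own AE definition, so events the participant does not blame on the product are not systematically solicited

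*Combined protocol and SAP*

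**What the plan says.** **Definition and relatedness.** Section 6.4 states: "Adverse Events (AEs) are defined as any untoward medical occurrences described by the study participant". Nothing in that sentence makes the event depend on the product. On the route of collection, the same section adds: "All AEs will be self-reported and documented on the platform". Section 6.4.2 assigns the causal judgement: "Each reported AE will be assessed by the Investigator for relatedness, severity and causality".

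**Prompts.** Section 6.1 says that after dosing "the participant will be instructed to fill out an Adverse Event form for any side-effects experienced". The diary in Appendix E closes with "Did you experience any side effects after taking the test product? (Y/N) If yes", and a yes sends the participant to the AE form. The AE form in Appendix G opens with "Did you experience any side effects after taking the test product", and its symptom checklist is introduced by "If so, did you experience any of the following". Items 3 to 5 of that form (timing, what was done to relieve it, hospital or doctor contact) again refer to the side effect.

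**Timing.** The schedule in Section 6.2 has a row labelled "AE Assessment". It is marked at each event, at 15, 30 and 60 minutes after it, and at study exit. The Study Exit Survey is a separate row, also marked at exit. The six items of the exit form in Appendix F cover experience with the product, perceived benefit, willingness to recommend it, open comments and avoided medication. None asks about adverse events.

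**Analysis.** The AE summary is listed among the secondary endpoints in Sections 3 and 7.1.

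**The concern.** In ordinary usage a side effect is something a product caused. A form that asks only about side effects invites the participant to settle causality before anything is written down, although Section 6.4.2 reserves that step for the investigator. The investigator can assess only what was reported.

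Misattribution is easy in this trial. The anticipated events in Section 6.4.1 include upset stomach and vomiting, which overlap with the condition being treated, so a participant may put them down to the indigestion and answer no. Section 11 acknowledges that symptoms receive no medical review, and the documents describe no second source, such as a clinic visit, that would pick up an omitted event.

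At stake is what the AE summary means. Collected in this way it is closer to a list of effects that participants attributed to the product than to a list of AEs as the protocol defines them, and it leans low. Notification of the investigator and sponsor under Section 6.4, and recognition of a serious event under Section 6.4.3, rest on the same entry point.

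**Working it through.** The plan states no AE rate, safety sample size or safety threshold, so there is no figure to reproduce. The check sets each step from definition to summary against the next.

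1. **What counts as an AE (Section 6.4).** Any unfavourable medical event that the participant describes. Attribution is not a condition.
2. **Who judges cause (Section 6.4.2).** The investigator, for each event reported. This presumes that unrelated events reach the investigator as well.
3. **When the form is to be used (Section 6.1).** For side effects. Narrower than step 1.
4. **What the diary asks (Appendix E).** About side effects after taking the product. Only a yes leads on to the AE form. Narrower than step 1.
5. **What the AE form asks (Appendix G).** The same question acts as a gate, and the checklist follows only on a yes. A participant who had, say, a rash blamed on something else, and who answers no, is not asked about rash. Items 3 to 5 keep the same wording.
6. **What happens at exit (Section 6.2 against Appendix F).** An AE assessment is scheduled. The exit form has no AE item, and no text says which instrument is used or who asks.
7. **Other contacts.** The weekly emails in Section 6.1 are reminders of participation. The contact after 30 days without event data in Section 6.5 asks about episodes and continuation. Neither is described as asking about AEs, while participation under Section 4.3 can last 60 days.

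Steps 3 to 5 all narrow in the same direction, and nothing in the forms shown widens the question again. An event that falls within step 1 but is not perceived as a side effect therefore has no form item that directly asks for it. That follows from the wording alone, without an assumed event rate.

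**The case against.** The strongest reply is that the forms are less restrictive than they look. The words about taking the product also convey timing, so some participants will report anything that follows a dose. Appendix G has a line for other events and asks for a free description. The diary rates nausea, vomiting, abdominal and chest pain and an open category before dosing and up to 60 minutes after it, whatever the cause. The definition in Section 6.4 governs, and the study is short, uncontrolled and descriptive, with no safety threshold to be crossed.

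Most of this stands, and it limits the point. Three stronger readings are tempting and are not supported:

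- **That unattributed events are never recorded.** Some will be, for the reasons just given. The documents support only that they are not systematically asked for.
- **That nothing prompts for an event after the last diary entry.** Section 6.2 schedules an exit AE assessment separately from the exit survey, and Appendix G could serve as its instrument. What is missing is a statement of how it is done. The product insert (Appendix H) and the consent form could not be checked and may carry wider instructions.
- **That the AE form is the only evidence on safety.** Worsening of the rated symptoms within the first hour is captured in the diary, although as efficacy data.

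A reader might also want a number. With no events among 97 treated participants, the exact interval planned in Section 7.3 would have a two-sided 95% upper limit of 1 − 0.025^(1/97) = 3.7%. That shows only what such an interval would describe, namely reported side effects. It does not say how many events are missed, and 97 is the treated number wanted for efficacy power, not a planned safety denominator.

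The reply does not remove the mismatch itself. The free-text and other lines sit behind the same gate, and the governing definition helps only if the forms apply it.

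**Conclusion.** The point holds as an inconsistency between the AE definition and the instruments that collect AEs. The Section 6.1 instruction, the Appendix E question, and the gate and items 3 to 5 of Appendix G ask only about side effects. They are narrower than Section 6.4 and pre-empt part of the assessment in Section 6.4.2. The likely result is under-reporting of events that participants do not blame on the product. Separately, the exit AE assessment is scheduled, but its method is not shown.

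No size is claimed, because the documents give neither an AE rate nor a share of events attributed to the product. The direction rests on one assumption: that at least some participants read side effect in its usual causal sense. The change is worth making before data are collected, since events that were not asked about cannot be reliably recovered later. It does not touch the efficacy analysis.

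**What to change.** - **Section 6.1 and Appendices E and G.** Replace the side-effect wording with one question, for example: *Since you first took the test product (or since your last report, if you have made one), have you had any new or worsened health problem, whether or not you think the product caused it? Do not count your usual indigestion or heartburn episodes unless they were worse than usual.* The reference period keeps out events before the first dose, and the exclusion keeps the condition under study from filling the AE log.
- **Appendix G.** Show the symptom checklist to every respondent instead of only after a yes, and replace side effect with event or problem in items 3 to 5.
- **Exit.** Add the same question to Appendix F, or state in Section 6.2 that Appendix G is administered at study exit.

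The cost is rewording a few electronic form items, one added exit item or one line on how the exit assessment is done, and one line in Section 6.1. The investigator will have somewhat more AE entries to review. Sample size, design and treatment rules are unaffected.

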6.4.1. Anticipated Adverse Events

Anticipated Adverse Events are complications that are known to be associated with the test product (in high doses exceeding recommended use):

- Headache
- Amenorrhea
- Upset Stomach
- Diarrhea
- Hives
- · Difficulty breathing
- Facial swelling
- Drowsiness
- Tiredness

Vomiting

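### The adverse event form does not prompt by name, at ordinary intensity, for 6 of the plan's 10 anticipated events, and it has no severity or resolution field

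*Combined protocol and SAP*

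**What the plan says.** Section 6.4 defines adverse events as "any untoward medical occurrences described by the study participant", with no intensity threshold, and states that "All AEs will be self-reported and documented on the platform". Section 6.4.1 says that "Anticipated Adverse Events are complications that are known to be associated with the test product", adds the qualifier "in high doses exceeding recommended use", and names ten: headache, amenorrhea, upset stomach, diarrhea, hives, difficulty breathing, facial swelling, drowsiness, tiredness and vomiting. Section 6.4.2 reads: "Each reported AE will be assessed by the Investigator for relatedness, severity and causality". It gives no grading scale. Section 7.1 makes a summary of adverse events one of the secondary endpoints.

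The collecting instrument is Appendix G. It opens with a yes/no question on any side effect. A yes leads to item 1a, a checklist of ten grouped lines followed by Other. Two of those lines are "itching, rash, hives, throat/lip/tongue swelling, wheezing" and "severe, persistent nausea, vomiting, diarrhea, or abdominal pain". The remaining items ask for a description, the time from dosing to the effect, what was done to relieve it, and whether a hospital or doctor was involved, with upload of any hospital papers. No item asks for a severity grade or whether the event resolved.

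**The concern.** The checklist covers mainly alarm symptoms and was not built from the plan's own list. It names slurred speech and one-sided weakness but not headache or drowsiness. Its gastrointestinal line sets an intensity threshold that the definition in Section 6.4 does not contain. A participant with one loose stool or mild drowsiness finds no line that fits and must choose to use Other or the description.

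This matters because nothing else in the plan asks in a structured way. Participation is remote (Section 4), and Section 11 concedes that symptoms have no medical review. The symptom diary asks one yes/no question and sends the participant to Appendix G. The schedule in Section 6.2 shows an adverse event assessment at study exit, but the exit form in Appendix F has no adverse event question. A low count of an anticipated event could then mean either that it was rare or that the form did not ask. The investigator's severity assessment would have little structured input. The statistical analysis plan that Section 7.3 defers to a later document cannot tabulate fields that were never collected.

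**Working it through.** The documents give no adverse event rate or precision target, so there is no planned figure to reproduce. The check is a term-by-term match of Section 6.4.1 against Appendix G item 1a.

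| Term in 6.4.1 | Nearest entry in Appendix G | Named at ordinary intensity? |
|---|---|---|
| Headache | none | no |
| Amenorrhea | none | no |
| Drowsiness | none | no |
| Vomiting | gastrointestinal line, severe and persistent | no |
| Diarrhea | gastrointestinal line, severe and persistent | no |
| Upset stomach | no item of its own; nausea and abdominal pain in the gastrointestinal line | no |
| Hives | allergic line | yes, grouped |
| Facial swelling | throat, lip or tongue swelling in the allergic line | in part, grouped |
| Difficulty breathing | shortness of breath (cardiac line), wheezing (allergic line) | yes, grouped |
| Tiredness | fatigue, in a line with yellowing skin/eyes and dark urine | yes, grouped |

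**Count on the natural reading** (the qualifier governs all four gastrointestinal terms): 3 absent + 3 only as severe and persistent = 6 of 10.

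**Sensitivity of the count:**
- Qualifier governs nausea only: vomiting and diarrhea become named, so 6 − 2 = 4 of 10, with upset stomach still lacking an item. If abdominal pain is then accepted as standing for upset stomach, the count is 3.
- Facial swelling treated as not named: 6 + 1 = 7 on the natural reading and 4 + 1 = 5 on the narrow one.
- Diary ratings of vomiting and upper abdominal symptoms credited as capture: 6 − 2 = 4 (headache, amenorrhea, drowsiness, diarrhea).
- Headache, amenorrhea and drowsiness are missing on every reading.

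**Grouping:** none of the ten has a line to itself. A tick on the allergic line does not separate itching from tongue swelling; only the description can.

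**Severity and outcome:** items giving a severity grade, 0; items on resolution or stop date, 0. The hospital/doctor question informs only events that reached medical care. Outcome is relevant because the definition of a serious event in Section 6.4.3 turns partly on permanent impairment.

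**Onset:** item 3 gives the time from dosing, and the diary gives the date of onset and the time the product was taken. Onset can be derived.

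**Possible size of an undercount (illustration; incidence and capture are assumptions).** Reported events = 97 treated × true incidence × capture:
- 2%: 97 × 0.02 = 1.9 true; capture of 50–100% shows 1.0–1.9.
- 5%: 97 × 0.05 = 4.9 true; capture of 50–100% shows 2.4–4.9.
- 10%: 97 × 0.10 = 9.7 true; capture of 50–100% shows 4.9–9.7.

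The loss runs from none to half only because that capture range was chosen. Nothing in the documents narrows it.

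**The case against.** The strongest reply is that the form excludes nothing. Every event meets the same unrestricted first question, which the diary repeats for each episode. The checklist comes only after a yes, ends in Other, and is followed by a request to describe the event. Events can be coded from that description. This stands: the unlisted events are unprompted, not shut out, and a reader who inferred that the form cannot capture them would be wrong.

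The anticipated list is also tied to doses above recommended use, and Section 2.2.1 says the same. The list is therefore not a forecast of what will be common here, and few such events may occur. That lowers the stakes. It does not explain why some terms the plan chose were carried to the form and others were not.

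The diary grades nausea, vomiting and upper abdominal discomfort from 0 to 3 before dosing and at 15, 30 and 60 minutes. This recovers some information, but as efficacy ratings within the first hour, with no rule that a worsening counts as an adverse event.

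Severity is the investigator's task and need not be self-graded. The investigator has the description, latency, action taken and any medical papers; Section 2.2.3 provides for routine review, and Section 4 allows telephone contact if required. So severity can be assessed. What is missing is a structured basis: no grade is collected, no scale is defined, and no follow-up call for adverse events is scheduled.

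Finally, the adverse event summary is descriptive, among analyses that Section 7.1 calls hypothesis generating. That limits the weight of the point, but the summary is still a named endpoint and the plan's main safety output.

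**Conclusion.** The point holds as a mismatch between Appendix G and Sections 6.4 to 6.4.2. On the natural reading, 6 of the 10 anticipated events are not prompted by name at ordinary intensity. Other defensible readings give 3 to 7, and three terms are absent on all of them. The other four are grouped with other signs, and there is no severity or resolution field. Milder events may be under-reported, and severity and outcome will rest mainly on free text.

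Two stronger readings are tempting and should be resisted. One is that the summary will undercount or is biased low: the documents give neither incidence nor reporting sensitivity, so neither the fact nor the size of an undercount is shown. The other is that onset is lost: it can be derived from item 3 and the diary. The conclusion rests on the wording of the form as printed and on one reading of where the qualifier applies. It does not depend on any assumed event rate. It does not touch the primary analysis or the sample size. It is an inexpensive improvement worth making before launch.

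**What to change.** In Appendix G item 1a, give each of the ten Section 6.4.1 terms its own box at any intensity, then keep the present alarm symptoms and Other. For each event reported, add mild/moderate/severe and resolved yes/no with a date. No separate onset field is needed.

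State in Section 6.4.2 that these fields are input to the investigator's assessment, which remains the investigator's, and define the three grades there. In Section 7.3 or the later analysis plan, specify that adverse events are tabulated by term, severity and outcome, counting participants.

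The cost is the re-layout of one electronic form and its paper copy, and about a minute more for each participant who reports an event. Prompting by name may also raise the counts, so the report should state that these terms were solicited.
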